#### Exclusion Criteria

- Patients already treated with MIBG-I.
- History of serious clinical or psychiatric illness that, due to clinical judgment, may pose a risk for participation in this study.
- Patients being treated with other protocols with experimental drugs.
- Patients who have had recent major surgery less than 4 weeks ago.
- Patients who received chemotherapy or other cancer therapy less than 3 weeks ago.
- Pregnant or lactating patients.
- Another synchronic neoplasia that requires systemic treatment.

#### **MIBG-I Treatment**

##### MIBG scintigraphy:

Scintigraphy with MIBG-I will be performed as the method of choice for research and identification of active anatomical sites of expression of norepinephrine

receptors; for the staging of PggF and for the assessment of theranostic eligibility of patients for treatment with high doses of MIBG-I.

All patients will receive and must follow preparation prior to the exam, making use of iodized solutions to block the physiological uptake of eventual free iodine by the thyroid. Patients will be interviewed prior to the administration of doses, obtaining information about the correct preparation and the possible use of drugs that could potentially interfere with the result.

The exams will be performed 24 hours after the intravenous administration of 1.0 mCi of MIBG-I, using the GE Discovery 640 or 630 Gamma Camera equipment where images of the entire body and those associated with anatomy (Spect\_CT) will be obtained, following the Nuclear Medicine protocols of the A.C.Camargo Cancer Center. The exam will be considered as presenting a positive result when the concentration observed in the 24-hour images is considered to be of moderate to severe degree and still in agreement with the target lesions to be treated. The results will be obtained through the individual reading of the exams by two or more nuclear physicians, with experience varying between 30 and 6 years, with doubts being resolved in consensus with the most experienced.

#### Treatment with high-dose MIBG-I

MIBG-I is a radioactive drug that emits Beta particles (0.61 MeV of energy) with a physical half-life of 8 days and a gamma-ray emitter of 364 keV of energy (which allows the performance of imaging tests), where metaiodobenzylguanidine is a norepinephrine analogue. MIBG-I is selectively concentrated in tissues enriched by adrenergic innervation (mainly tissues of neuroectodermal origin, which include neuroectodermal neoplasms such as NET. MIBG-I enters cells through diffusion passive or by neuronal uptake mechanism and is stored in neuro-secretory granules. Unlike noraepinephrine, MIBG-I131 is not metabolized, which allows its intracellular retention for many days, making its theranostic use feasible; it is excreted in its entirety via the urinary tract. The mechanism of antitumor action occurs by the emission of ionizing radiation from the decay of I131; 90% of this radiation comes from the emission of Beta radiation, which has an average penetration of 0.5 mm in the tissues.

The main adverse effect of MIBG-I is myelotoxicity, which occurs between 4 to 6 weeks after MIBG-I131, with variable frequency according to heterogeneous studies (20-70% of all grades). Acute adverse events are of low intensity and include mild nausea and fatigue, elevated blood pressure (described in patients with PggF). Late events: hypothyroidism could occur if preventive measures described below are not taken; Persistent myelosuppression is uncommon and has been described in pre-treated patients with many previous regimens and chemotherapy (this treatment is uncommon in TNE); myelodysplasia, renal dysfunction or any other organ are considered to be rare and have no proven causality. The absolute contraindications are severe renal failure that requires dialysis, pregnancy/lactation and life expectancy less than 3 months; Relative contraindications are: moderate renal failure, refractory and resistant urinary tract infection, myelosuppression (serum platelet levels less than 100,000/mm^3 and total leukocytes less than 3,000/mm^3). Given the teratogenic potential, women of childbearing potential should undergo contraceptive measures during and for at least 4 months after treatment.

MIBG-I is administered at a dose of 200mCi intravenously every 8 weeks for up to 4 cycles. Laboratory tests are performed every 15 days, with a focus on assessing myelotoxicity. Laboratory blood tests within the appropriate results (see “inclusion criteria”) allow the administration of the next cycle. In the case of any toxicity with a degree equal to or greater than 3 or intolerable and persistent grade 2 toxicity, the next course of treatment will not be administered until the toxicity is grade 1 or resolves. If the toxicity does not resolve or becomes grade 1 within 8 weeks, the next cycle is not administered, and treatment is stopped.

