#### Administration protocol with MIBG-I

The treatments will be carried out in the Radioisotope Therapy Unit of the A.C.Camargo Cancer Center, which complies with the regulatory standards of the CNEN (National Nuclear Energy Commission) for treatments with radioisotopes and is part of the institutional routine.

After admission, patients will be evaluated by anamnesis, will receive radiological safety instructions and sign the consent form for the procedure, then be

prepared with venepuncture, placement of infusion and hydration equipment with saline, medication with antiemetics (ondansetron) and the collection of control exams.

The dose of MIBG-I provided by IPEN (Energy and Nuclear Research Institute - CNEN -SP) will be unpacked and its content and radioactive activity checked by the Nuclear Physician responsible for the procedure. The verified and authorized dose will be connected to the infusion equipment properly shielded from radiation and administered slowly between 45 and 180 minutes, under constant heart rate and blood pressure monitoring. Increases in blood pressure should be followed by stopping or slowing down the administration of the dose or/and using beta-blockers until normalization. The discharge will occur after the rate of radiological exposure produced by the patient is reduced to outpatient levels, which occurs within a maximum of 24 hours.

The bone marrow is the organ that receives the highest dose of unwanted radiation originating from the procedure, and during follow-up in cases of any toxicity with a degree equal to or greater than 3 or intolerable and persistent degree 2 toxicity, the next treatment cycle will not be administered until the toxicity is grade 1 or resolves; if it does not run within 8 weeks, treatment is stopped. Women of childbearing potential should use contraception for 6 months and men should consider using a sperm bank.

Thyroid protection is recommended so that it does not absorb radioactive iodine, with the ingestion of potassium chloride syrup twice a day, which begins 72 hours before MIBG-I and continues for 72 hours after treatment. This procedure is routine in the Nuclear Medicine service.

Guidance on hospital discharge, the participant/patient and their family members/caregivers on safety and radiation protection will be done according to the institution's routine.

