### **Security Assessments**

#### **Baseline Assessments:**

After signing the informed consent form, patients will be submitted to the baseline eligibility assessment (see Table 2).

Within 6 weeks of the first treatment dose: search for noraepinephrine expression by MIBG-I scintigraphy. If positive, eligibility is confirmed, and the following procedures are:

- Within 4 days of D1C1: Medical history, including previous diagnosis and treatment, history of other diseases (active and resolved), medications in use and general demographic data. Complete physical examination, ECOG performance index (PS) and vital signs.
- Within 4 days of the first treatment dose, laboratory tests will be performed: blood count, urea, creatinine, ALT, AST, total bilirubin, sodium, potassium, and pregnancy test for women of childbearing age; these patients will be oriented to contraception.
- Baseline imaging exams performed within 8 weeks of the first treatment dose will be accepted: CT scan (or MRI, if applicable) of the abdomen, pelvis and chest.
- For patients with functioning NET, it will be accepted that baseline tumor marker exams have been performed within 8 weeks of the first treatment dose (eg 5HIAA in 24-hour urine).

With the exception of MIBG scintigraphy, which is used routinely for patients with PggF (but not TNE), all of the above tests are already part of the routine in the treatment of NET at A.C.Camargo Cancer Center.

*Safety assessments during treatment:*

Patients will be evaluated clinically and with laboratory tests (Table 2) every 15 days between treatment cycles and after completion until resolution of any adverse treatment effects. +/- 3 days window will be allowed.

- Complete physical examination, measurement of vital signs, weight measurement, ECOG, use of medications.
- Assessment of adverse events.
- Laboratory evaluation: blood count, urea, creatinine, ALT, AST, total bilirubin, sodium, potassium, and others, if clinically indicated.

To grade toxicities we will use the CTCAE 5.0 criteria. Patients who have intolerable grade 2 or grade 3 toxicity that the investigator deems to be related to MIBG-1131 will have their treatment cycle delayed to grade 1 or resolution. If there is no reduction in the intensity of the adverse event to grade 1 within 8 weeks, treatment is discontinued.

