Laboratory safety assessment												
Hemogram	X	X	X	X	X	X	X	X	X	X	X	
Urea/creatinine	X	X	X	X	X	X	X	X	X	X	X	
Bilirubin, AST/ALT	X	X	X	X	X	X	X	X	X	X	X	
NA, K	X	X	X	X	X	X	X	X	X	X	X	
Pregnancy test in women of childbearing age		X										
Image assessment												
CT of lung, abdomen and pelvis ***	X							X			X	X
Tumor marker **												
Specific hormone		X						X			X	X
Quality of life **												
EORTC QLQ-C30		X						X			X	X
EORTC QLQ-GINET21		X						X			X	X

IV, intravenous; MIBG, metaiodobenzylguanidine

\* within 6 weeks of the first dose and within 4 working days of D1;

\*\* window of +/- 3 days

\*\*\* baseline tests within 8 weeks of D1; Resonance of the abdomen and pelvis in special cases (allergy to iodinated contrast); window +/- 5 days

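### Hypothyroidism is named as a late event if prevention fails, but no thyroid test is scheduled, so it would be under-ascertained and a zero count would not show absence

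*Combined protocol and SAP*

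**What the plan says.** - **Risk.** The section on treatment with high-dose MIBG-I131 opens its list of late effects with "Late events: hypothyroidism could occur if preventive measures described below are not taken". The risk is conditional on prevention.
- **Prevention.** For the diagnostic scan, the MIBG scintigraphy section has patients "making use of iodized solutions to block the physiological uptake of eventual free iodine by the thyroid". For therapy, the administration protocol recommends thyroid protection "with the ingestion of potassium chloride syrup twice a day, which begins 72 hours before" treatment and continuing for 72 hours after it, and calls this routine.
- **Baseline laboratory tests** (Baseline Assessments): "blood count, urea, creatinine, ALT, AST, total bilirubin, sodium, potassium, and pregnancy test for women of childbearing age".
- **On-treatment laboratory tests** (safety assessments during treatment): "Laboratory evaluation: blood count, urea, creatinine, ALT, AST, total bilirubin, sodium, potassium, and others, if clinically indicated". The treatment section gives their purpose: "Laboratory tests are performed every 15 days, with a focus on assessing myelotoxicity".
- **Table 2.** The laboratory block has rows for hemogram, urea/creatinine, "Bilirubin, AST/ALT", sodium and potassium, and a pregnancy test. The one hormone row sits under tumor markers.
- **At admission for therapy.** The administration protocol mentions "the collection of control exams" without itemising them.
- **Safety outcome.** Secondary outcome 6 concerns treatment-related adverse events and counts those of CTCAE grade 2 or higher.

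**The concern.** The plan identifies a specific late toxicity of its study drug, gives up to four doses of 200 mCi, and then schedules no measurement that could show that toxicity. What gets recorded depends on whether someone thinks to test. Fatigue, one complaint that might prompt a test, is already listed as an expected acute effect and so is easily explained away.

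At stake is how the tolerability results can be read. A low or zero count of hypothyroidism could mean that it did not occur or that it was not looked for, and the data would not separate the two. For any case that is found, the lack of a baseline value weakens the judgement of whether it is new and whether treatment caused it.

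**Working it through.** The plan states no figure on this point, so there is none to reproduce. The check is mainly of the text.

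**1. Is a thyroid test scheduled anywhere?** The baseline list, the on-treatment list and the Table 2 laboratory block agree with each other: blood count, renal tests, liver tests, electrolytes and a pregnancy test. None includes TSH, T4 or another thyroid test. The hormone row in Table 2 is the marker for functioning syndrome, as secondary outcome 4 makes clear. The admission tests are not itemised, so their content cannot be verified.

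**2. When do scheduled laboratory tests stop?** As the table was extracted, its laboratory rows carry no mark in the last column (every 12 or 8 weeks), although physical examination, symptoms and adverse events do. Study design says the two-weekly checks run until toxicities resolve, usually 30 days after treatment. The Abstract has two-weekly laboratory tests throughout the study, but names no thyroid test either. On the table's reading, laboratory cover is thinnest when a late event would be expected.

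**3. What do the adverse event rules need?** The safety section defines an adverse event as a condition that appears, or a pre-existing one that worsens, after consent. Whenever possible, it asks for the relationship to study drug and for start and end dates. A baseline value bears on all three judgements: new or worsened, related or not, and date of onset.

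**4. Is the preventive condition secure?**

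| | Diagnostic scan | Therapy |
|---|---|---|
| Agent named for thyroid blocking | Iodized solutions | Potassium chloride syrup |
| Force of the instruction | Patients must follow the preparation | Protection is recommended |
| Check on adherence | Interview about correct preparation | History taken at admission; no explicit check on blocking |

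The database fields listed in Study design do not include adherence to blocking. Because the protocol makes the risk depend on this measure, the two sections must be reconciled. Which agent is intended is for the sponsor to say.

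**5. Illustration of size.** The documents give neither a hypothyroidism rate nor a detection rate, so both are assumptions. With N = 22 (Statistical plan), true incidence r and detected share s, the chance of recording no case is (1 − r × s)^22.

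| True incidence r | s = 1 | s = 0.5 | s = 0.25 |
|---|---|---|---|
| 5% | 0.95^22 = 32% | 0.975^22 = 57% | 0.9875^22 = 76% |
| 10% | 0.90^22 = 10% | 0.95^22 = 32% | 0.975^22 = 57% |
| 20% | 0.80^22 = 0.7% | 0.90^22 = 10% | 0.95^22 = 32% |

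Even with full detection, 0 of 22 has a one-sided 95% upper limit of 1 − 0.05^(1/22) = 12.7%. That holds for any event in 22 patients. It shows how little a zero could establish at best, and does not measure the effect of the missing test.

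**The case against.** The strongest reply is that the plan has other routes to detection. Adverse events are sought by indirect questioning at every visit and can also come from voluntary reports, examination or laboratory tests. The laboratory list leaves room for further tests on clinical indication, and adverse event assessment continues in the last column of Table 2. Clinically apparent hypothyroidism can therefore be found and recorded. This stands. A reader might infer that the trial would report hypothyroidism as absent, or that zero recorded cases would carry no information. The documents support neither: a zero would still say something about clinically apparent disease.

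Four further points on that side:

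- **The risk is conditional on prevention, which is called routine.** True, and the point has to carry that condition. But the text does not settle what the preventive measure is, so the condition cannot dispose of the issue.
- **The outcome counts only grade 2 or higher.** True. Whether a symptomless abnormal value would enter it depends on CTCAE grading, which the documents do not reproduce. The lack of a baseline value still affects cases that do qualify.
- **Attribution and dating remain possible.** Baseline history covers active and resolved diseases and current medication, and each event gets a causality judgement. So attribution is made harder, not impossible.
- **Little depends on it.** Tolerability is the last secondary objective, safety is reported descriptively, laboratory monitoring is openly aimed at myelotoxicity, and no thyroid-safety claim is planned. This limits the weight of the point but does not remove it.

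**Conclusion.** The point holds as a minor one. No thyroid test is scheduled at any time, detection rests on clinical suspicion, and there is no baseline value. Hypothyroidism would be under-ascertained, and a zero count would not be evidence of absence. The extent cannot be computed from the documents. Under the assumed values above, a zero becomes more likely as detection falls (from 10% to 57% at a true incidence of 10%), but it is never certain while some cases are detected.

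The conclusion assumes that the unitemised admission tests contain no thyroid test and that the extracted Table 2 shows the schedule correctly. If the admission tests do include one, the sponsor need only say so.

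Two stronger readings should be set aside. A reader might infer that the treatment section contradicts Table 2; it does not, because that section promises no thyroid testing and the gap is an omission. A reader might also infer that the whole tolerability conclusion is unsound; the weakness is confined to thyroid toxicity. The one real inconsistency is between the two descriptions of thyroid blocking.

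**What to change.** - Add a thyroid function row to the laboratory block of Table 2, at baseline and at already scheduled visits that the sponsor's clinicians choose, and match it in the laboratory lists under Security Assessments.
- Report abnormal values descriptively. Count them in secondary outcome 6 only if they reach grade 2 or higher, so that the outcome definition is unchanged.
- If testing is not added, state that hypothyroidism was ascertained only on clinical suspicion, and make no claim of thyroid safety.
- In either case, reconcile the thyroid-blocking text in the MIBG scintigraphy section with that in the administration protocol.

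**Cost.** One assay, which at baseline uses blood already drawn. Follow-up at 12 weeks may need an added sample, because Table 2 marks no laboratory tests there. The reporting alternative costs one sentence.

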#### Administration protocol with MIBG-I

The treatments will be carried out in the Radioisotope Therapy Unit of the A.C.Camargo Cancer Center, which complies with the regulatory standards of the CNEN (National Nuclear Energy Commission) for treatments with radioisotopes and is part of the institutional routine.

After admission, patients will be evaluated by anamnesis, will receive radiological safety instructions and sign the consent form for the procedure, then be

prepared with venepuncture, placement of infusion and hydration equipment with saline, medication with antiemetics (ondansetron) and the collection of control exams.

The dose of MIBG-I provided by IPEN (Energy and Nuclear Research Institute - CNEN -SP) will be unpacked and its content and radioactive activity checked by the Nuclear Physician responsible for the procedure. The verified and authorized dose will be connected to the infusion equipment properly shielded from radiation and administered slowly between 45 and 180 minutes, under constant heart rate and blood pressure monitoring. Increases in blood pressure should be followed by stopping or slowing down the administration of the dose or/and using beta-blockers until normalization. The discharge will occur after the rate of radiological exposure produced by the patient is reduced to outpatient levels, which occurs within a maximum of 24 hours.

The bone marrow is the organ that receives the highest dose of unwanted radiation originating from the procedure, and during follow-up in cases of any toxicity with a degree equal to or greater than 3 or intolerable and persistent degree 2 toxicity, the next treatment cycle will not be administered until the toxicity is grade 1 or resolves; if it does not run within 8 weeks, treatment is stopped. Women of childbearing potential should use contraception for 6 months and men should consider using a sperm bank.

Thyroid protection is recommended so that it does not absorb radioactive iodine, with the ingestion of potassium chloride syrup twice a day, which begins 72 hours before MIBG-I and continues for 72 hours after treatment. This procedure is routine in the Nuclear Medicine service.

Guidance on hospital discharge, the participant/patient and their family members/caregivers on safety and radiation protection will be done according to the institution's routine.

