## **Methodology**

### **Study design**

This is a single-arm, unicentric, single-stage, phase 2 clinical study of therapeutic metaiodobenzylguanidine (MIBG) for patients with metastatic well-differentiated neuroendocrine tumors and radiological progression or intolerance after standard lines of treatment and with MIBG-I positive scan.

Eligible patients will receive MIBG-I in up to 4 doses of 7,400Mbq (200 mCi) each, with an interval of at least 60 days. The administration of the cycles will depend on the results of the haematological exams, therefore, each patient will be able to receive from 1 to 4 cycles; In the experience of A.C.Camargo Cancer Center, most patients receive between 3 and 4 cycles. MIBG-I is administered intravenously to an inpatient, being discharged when reaching limits of radiological exposure recommended by the National Nuclear Energy Commission (invariably, 24 hours). The dose of 200mCi

per application for up to 4 doses of MIBG-I used in this protocol is the same used in routine at the institution and is also used in other PPRT treatments. This dose is safe and practiced by the service for at least a decade.

Clinical and toxicity assessments will take place every 2 weeks with medical history, physical examination and general laboratory until resolution of toxicities (usually 30 days after treatment). Imaging exams (chest, abdomen and pelvis CT scans) and 5-HIAA dosage in 24-hour urine (functioning tumors) will be performed at the beginning of treatment, and every 3 months until progression or exit from the study. Symptom assessment will be conducted using quality of life questionnaires that will be administered before treatment and every 3 months until progression. Toxicities will be measured in all medical visits through CTCAE version 5.0. Consultations, laboratory and imaging tests are already part of the treatment routine of these patients. The extra routine interventions, that is, the study, are the MIBG-I scintigraphy exam, the treatment with MIBG-I and the quality-of-life assessments.

Clinical data will be prospectively collected in an electronic database (REDCap) and will include sex, age, primary tumor site, performance scale status, functionality, metastatic disease duration, metastasis sites, degree of liver impairment, comorbidities, previous treatments, scores of quality of life results and toxicity.

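### The protocol names potassium chloride syrup, which contains no iodine, as the only thyroid protection with therapeutic MIBG-I131; the agent needs correcting

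*Combined protocol and SAP*

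**What the plan says.** The instruction for the therapeutic doses is in the section Administration protocol with MIBG-I131: "Thyroid protection is recommended so that it does not absorb radioactive iodine, with the ingestion of potassium chloride syrup twice a day". It starts 72 hours before the dose "and continues for 72 hours after treatment", and the section adds: "This procedure is routine in the Nuclear Medicine service".

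Three other places bear on it:

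- Treatment with high-dose MIBG-I131, in its account of late events, says "hypothyroidism could occur if preventive measures described below are not taken". The same section gives the regimen: MIBG-I131 "is administered at a dose of 200mCi intravenously every 8 weeks for up to 4 cycles".
- MIBG scintigraphy describes patient preparation for the diagnostic scan as "making use of iodized solutions to block the physiological uptake of eventual free iodine by the thyroid". The images are taken "24 hours after the intravenous administration of 1.0 mCi" of the tracer.
- Study design says of the 200 mCi dose: "This dose is safe and practiced by the service for at least a decade".

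**The concern.** The sentence states its purpose, which is to keep radioactive iodine out of the thyroid, and then names a compound made only of potassium and chlorine. The agent does not match the purpose.

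This is an operative instruction, with an agent, a frequency and start and stop times. Someone who followed it to the letter would give therapeutic I-131 without the protection on which the protocol relies to avoid hypothyroidism.

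Scheduled monitoring would not readily reveal the failure. The laboratory panel in Security Assessments and Table 2 contains no thyroid function test; one could be added only where clinically indicated. Hypothyroidism is classed as a late event, whereas the two-weekly toxicity visits continue only until toxicities resolve, which Study design puts at usually 30 days after treatment. This is context for why prevention should be stated correctly, not a request for an extra test.

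**Working it through.** No statistical figure is involved, so the check consists of setting side by side every place that mentions thyroid protection.

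| Place | Procedure covered | Stated purpose | Agent named |
|---|---|---|---|
| MIBG scintigraphy | Diagnostic scan, 1.0 mCi | Block thyroid uptake of free iodine | Iodized solutions |
| Treatment with high-dose MIBG-I131 | Therapy | Avoid hypothyroidism | None; refers to measures further down |
| Administration protocol with MIBG-I131 | Therapy, 200 mCi per dose | Stop the thyroid taking up radioactive iodine | Potassium chloride syrup |
| Table 2 | Whole schedule | Not mentioned | None |

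**Step 1: can the agent serve the purpose?** Potassium chloride is KCl. It supplies no iodine, so it cannot provide the iodine blockade that the scintigraphy section describes.

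**Step 2: does another passage correct it?** The high-dose section points forward, and the only thyroid measure after that point is the potassium chloride sentence. The iodized solutions belong to the preparation for the scan and are not carried over to treatment. The two sections concern different procedures, so they do not strictly contradict each other. They share a purpose, however, and the scan section shows what class of agent was probably meant.

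**Step 3: which procedure carries the wrong agent?**

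- Activity per therapeutic dose relative to the scan: 200 mCi / 1.0 mCi = 200.
- Total therapeutic activity over 1 to 4 cycles: 1 × 200 = 200 mCi to 4 × 200 = 800 mCi; equivalently 1 × 7,400 = 7,400 MBq to 4 × 7,400 = 29,600 MBq.

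The error thus sits with the higher-activity procedure. These are administered activities; they are neither thyroid doses nor risks, and they say nothing about how often harm would occur.

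**Step 4: can the harm be sized?** No. The documents give no hypothyroidism rate with or without blocking.

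**The case against.** The strongest reply is that this is a slip of the pen that no patient would ever experience. Treatment is given in one specialised unit under a nuclear physician, the thyroid procedure is described as routine there, the dose has a decade of local use, and the same service evidently blocks with iodized solutions before scans. Other wording in the protocol also reads like translation from Portuguese, such as TNE in place of NET. On that view a minor correction would be a fair grade. The low likelihood of harm stands. It does not make the written drug instruction correct, and new staff, pharmacists, ethics reviewers or another centre adopting the regimen would read the wrong drug.

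Two narrower objections have some force:

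- The text does not say that protection is repeated with each cycle, but its timing is tied to the administration, so the natural reading is that it accompanies every dose. Saying so explicitly is a clarification rather than the repair of a defect.
- The documents do not say what the service actually gives with therapy. The inference to an iodine-containing agent comes from the scan section, so the service must confirm the product and dose.

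Neither objection rescues potassium chloride.

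**Conclusion.** The concern holds. The only thyroid-protection instruction for therapeutic MIBG-I131 names an agent that cannot do what the sentence asks, and nothing else in the protocol corrects it. It should be fixed: it is a definite error in a safety instruction, with a low probability of actual harm and almost no cost to correct. Confidence in the error is high, because it follows from the composition of the named compound and a reading of the whole document.

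Two inferences remain: that the cause is a wording or translation slip, and that an iodine-containing agent was intended. The first is supported by the description of the procedure as routine, the second by the scintigraphy section; neither is stated outright. The primary outcome, sample size and analysis do not change.

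**What to change.** In Administration protocol with MIBG-I131, replace potassium chloride syrup with the iodine-containing blocking agent that the nuclear medicine service uses, as confirmed by that service, and give its dose. The service should confirm at the same time that the twice-daily frequency and the 72-hour margins apply to the agent named. Adding that the protection is given with every therapeutic cycle is a useful clarification in the same sentence.

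The cost is a wording amendment to one sentence. It requires no new test, visit, schedule change or funding.
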